	
increase in PGA (VAS)
 
 – No protocol-prohibited medication or treatment. – Concomitant corticosteroid dosage at Week 24 to be \leq10 mg/day – Concomitant corticosteroid dosage at Week 24 to be \leqDay 1 corticosteroid dosage – No increase in corticosteroid dose between Weeks 17 and 24 
 • Change from baseline to Week 24 in SLEDAI-2K score • Proportion of subjects with no new organ system affected, as defined by no new BILAG-2004 A and no more than one new BILAG-2004 B from baseline to Week 24 • Change from baseline to Week 24 in PGA VAS score
To evaluate pharmacokinetic parameters of BIIB059 (Parts A and B)	
 • BIIB059 clearance, volume of distribution, and absorption rate
To evaluate the safety and tolerability of BIIB059 (Parts A and B)	
 • Nature, severity, relationship to study treatment and incidence of AEs and SAEs • Change from baseline in standard laboratory parameters, vital signs and ECGs • Immunogenicity (antibodies to BIIB059) • Absolute and percent change from baseline over time in immunoglobulin levels and vaccine-related immunoglobulin titers
 	
 •  •  •  •  • 

CONFIDENTIAL

The information contained herein may not be used, disclosed, or published without the written consent of
Biogen MA Inc.

[REDACTED]	
• [REDACTED]• [REDACTED]• [REDACTED]• [REDACTED]• [REDACTED]• [REDACTED]• [REDACTED]• [REDACTED]• [REDACTED]• [REDACTED]
[REDACTED]	
• [REDACTED]• [REDACTED]• [REDACTED]• [REDACTED]• [REDACTED]
[REDACTED]	
• [REDACTED]• [REDACTED]• [REDACTED]• [REDACTED]• [REDACTED]
[REDACTED]	
• [REDACTED]• [REDACTED]
[REDACTED]	
• [REDACTED]• [REDACTED]

CONFIDENTIAL

The information contained herein may not be used, disclosed, or published without the written consent of
Biogen MA Inc.

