For a list of commonly used topical corticosteroids that are not permitted during the study, see [Appendix B](#). The Investigator is invited to contact the Sponsor's Medical Monitor with questions about topical corticosteroid use during the study.

11.4.1.1.2.2. Part A Specific Instructions

Intra-articular Corticosteroids

Intra-articular administration of corticosteroids is not allowed for the duration of the study; a washout period of 12 weeks must be observed prior to randomization.

Oral Corticosteroids

Eligible subjects will have active SLE with joint and skin manifestations at Screening and randomization. Subjects may be treated with SLE background SoC therapies as per exclusion criterion #31 and, if taking corticosteroids, must have been on stable dosage for at least 4 weeks prior to randomization. Subjects who are not receiving corticosteroids at Screening or baseline are permitted to participate in the study.

Doses of corticosteroid must remain stable during Screening and during the first 4 weeks after the first dose of study treatment (i.e., until Day 28). The tapering schedule should begin 4 weeks (Week 5; Days 29 to 35) after the first dose of study treatment. The tapering regimen is intended to reduce the daily dose of prednisone (or equivalent) to 10 mg/day or lower by Week 12 (Day 85) of the study, as outlined in [Table 7](#).

If a subject deviates from the planned tapering schedule, they might be considered a treatment failure (see Section [16.1.2.1](#)). Subjects are allowed to continue to receive the investigational product and to complete the study at the discretion of the Investigator.

Subjects who achieve the Week 12 dose of 10 mg of prednisone (or equivalent) or lower may remain on this dose or continue to taper between Week 13 and Week 16 at the discretion of the Investigator. The dose of prednisone (or equivalent) will remain stable (at the Week 16 dose) between Week 17 and Week 24.

Screening:

Subjects who are receiving corticosteroids must receive a stable dose throughout the Screening period; no initiation, increase, or decrease of corticosteroid dose is permitted.

CONFIDENTIAL

The information contained herein may not be used, disclosed, or published without the written consent of Biogen MA Inc.

The maximum daily dose of corticosteroid allowed is 20 mg of prednisone (or equivalent).

Treatment period:

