Oral corticosteroid dose tapering (as described in [Table 7](#)) is mandatory within the rules for dose changes outlined below.

Briefly, oral corticosteroids dosing guidelines are as follow:

- Stable corticosteroid dose from Day 1 to Week 4 (Day 1 to Day 28)
- Decrease in corticosteroid dose from baseline between Week 5 and Week 11 (Days 29 to 78)
- Stable corticosteroid dose at Week 12 (Days 79 to 85)
- Stable Week 12 corticosteroid dose, or decrease by 2.5 mg between Week 13 and Week 16 (Day 86 to 113)
- Stable corticosteroid dose (at Week 12 dose) between Week 17 and Week 24 (Days 114 to 169)

Between Day 1 to Week 4, the corticosteroid dose can be increased to a maximum of 10 mg/day above Day 1 dosage, but must return to Day 1 level within 7 days (Rescue 1). Between Week 5 and Week 7 (Rescue 2), OR between Week 9 and Week 11 (Rescue 3), the corticosteroid dose can be increased to the previous dosage level for up to 1 week before resuming the tapering schedule. Only two rescues out of the three described above are allowed, at the discretion of the Investigator.

Overall, TWO corticosteroid rescues are allowed:

- Rescue 1 and Rescue 2; OR
- Rescue 1 and Rescue 3; OR
- Rescue 2 and Rescue 3.

Any other increase in corticosteroid dose may be considered a treatment failure and/or a protocol deviation (depending on the timing or severity of the deviation) for the analysis (see [Section 16.1.2.1](#)). Subjects who cannot fulfill the corticosteroid tapering schedule should still complete the study and remain on the investigational product. Corticosteroid dose should be recorded in the subject diary ([Section 11.4.1.1.2.4](#)).

Day 1 to Week 4:

Stable dosage at Day 1 dose level, 1 oral corticosteroid rescue (Rescue 1) for SLE activity is allowed up to a dose no higher than 10 mg above the baseline level (maximum of 30 mg/day), but the dose must return to baseline (Day 1) level within 7 days. A dose increase is strongly recommended to be avoided within 1 week of a planned study visit.

Week 5 to Week 7:

Decrease as per the tapering schedule. One oral corticosteroid rescue (Rescue 2) for SLE activity is allowed up to a dose no higher than the previous dosage level, but the dose must be

CONFIDENTIAL

The information contained herein may not be used, disclosed, or published without the written consent of Biogen MA Inc.

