returned to the last oral corticosteroid dosage prior to rescue level within 7 days. A dose increase is not permitted within 1 week of a planned study visit.

Week 8:

Decrease as per tapering schedule. No increases are allowed.

Week 9 to Week 11:

Decrease as per tapering schedule. One oral corticosteroid rescue (Rescue 3) for SLE activity is allowed up to a dose no higher than the previous dosage level, but the dose must be returned to last oral corticosteroid dosage prior to rescue level within 7 days. A dose increase is not permitted within 1 week of a planned study visit.

Week 12:

No increase or decrease allowed.

Week 13 to Week 16:

Stable dosage or decrease as per the tapering schedule (no increase is allowed). The corticosteroid dose must always be \leq Week 12 dose.

Week 17 to Week 24:

Stable dosage at Week 16 dosage, no increases or decreases are allowed.

CONFIDENTIAL

The information contained herein may not be used, disclosed, or published without the written consent of
Biogen MA Inc.

Table 7: Oral Corticosteroid Tapering Schedule

Allowable OCS Rescue Dosing ¹	Timing by Weeks (Days)	OCS Starting Dose Prior to Tapering (mg/day)							
		20 mg	17.5 mg	15 mg	12.5 mg	10 mg	7.5 mg	5 mg	2.5 to <5 mg
Rescue 1	Week 1-4 ² (Day 1 to 28)	Stable 1 OCS rescue for SLE activity allowed up to maximum 10 mg/day above Day 1 dosage, but must return to Day 1 level within 7 days							
Rescue 2	Week 5 ³ (Day 29 to 35)	17.5	15	12.5	10	7.5	5	5 or 2.5	2.5 to <5
	Week 6 ³ (Day 36 to 43)	17.5	15	12.5	10	7.5	5	5 or 2.5	2.5 to <5
	Week 7 ³ (Day 44 to 50)	15	12.5	12.5	10	7.5	5	5 or 2.5	2.5
	Week 8 (Days 51 to 57)	15	12.5	10	7.5	7.5	5	5 or 2.5	2.5
Rescue 3	Week 9 ³ (Days 58 to 64)	12.5	10	10	7.5	5	2.5	2.5	0 to 2.5
	Week 10 ³ (Days 65 to 71)	12.5	10	10	7.5	5	2.5	2.5	0 to 2.5
	Week 11 ³ (Days 72 to 78)	10	7.5	7.5	5	2.5 to <5	2.5	2.5	0 to 2.5
	Week 12 (Days 79 to 85)	10	7.5	7.5	5	2.5 to <5	2.5	2.5	0 to 2.5
	Week 13-16 (Days 86 to 113)	Stable at Week 12 dose or decrease							
	Week 17-24 (Days 114 to 169)	Stable at Week 16 dose							

Abbreviations: OCS = oral corticosteroids; SLE = systemic lupus erythematosus.

¹ Two rescues are allowed out of the three described.

CONFIDENTIAL

The information contained herein may not be used, disclosed, or published without the written consent of Biogen MA Inc.

² Between Weeks 1 and 4 (Rescue 1). Once a dose is reduced it must not be re-increased, with the exception of the 1 time rescue.

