5.8. Treatment Failure

For each part below, subjects who meet any of the following criteria will be considered as a treatment failure and considered as a non-responder in the efficacy analysis:

Part A

- Subjects who initiate or increase SLE standard of care therapy or other disallowed concomitant therapy (Table 8 of the latest protocol version) during the treatment period of the study.
- Subjects with corticosteroid dose increase above baseline during the treatment period except for what is allowed under rescue 1 during week 1 to 4.
- Subjects with more than 2 allowed rescues between week 1 to week 12.
- Subjects with any increase in corticosteroid during treatment period after week 20.

CONFIDENTIAL

The information contained herein may not be used, disclosed, or published without the written consent of Biogen MA Inc.

Part B

- Subjects who initiate disallowed concomitant therapy during treatment period of Part B (see Table 8 of the latest protocol version).
- Subjects who initiate or increase SLE/CLE standard of care therapy during the treatment period of the study.
- Subjects who initiate or increase corticosteroid dose above baseline during the treatment period of the study (oral or topical except those in Table 6 of the latest protocol version).

Note: Treatment failure subjects would be allowed to remain in the trial and receive investigational product, as applicable)

More detailed definition regarding specific concomitant therapy is described in and addendum to this SAP. For both parts, subjects' data considered as treatment failure will be handled as described in [Section 6.6](#).

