The reduction from baseline to Week 12 and 16 in the CLASI-A score will be calculated for each subject. The proportion of subjects who had ≥ 7 -point CLASI-A response at week 12 or week 16, defined as a ≥ 7 -point reduction in the CLASI-A score from baseline at week 12 or 16, will be analyzed separately for each time point as described for binary endpoint in [Section 6.1.2](#).

CONFIDENTIAL

The information contained herein may not be used, disclosed, or published without the written consent of Biogen MA Inc.

 Biogen	Statistical Analysis Plan 230LE201	<V 2.0>
--	---	----------------------

6.3.4. Percent Change in CLASI-A Score from Baseline at Week 12, 16 and 24 (Part A) and Week 12 (Part B)

The change from baseline to each post-baseline week in the CLASI-A score will be analyzed will be analyzed as described for continuous endpoint analysis in [Section 6.1.1](#) (Part A) and [Section 6.1.2](#) (Part B). Summary statistics for actual values and change from baseline will also be presented by week based on observed data.

6.3.5. Proportion of Subjects with an SLE Responder Index (SRI) Response of ≥ 4 at Week 24 (Part A Only)

SLE Responder Index (SRI) of ≥ 4 (SRI-4) at Week 24 is a categorical response variable (yes/no) incorporating the following criteria for achievement of responder status (i.e., all criteria must be met to achieve responder status):

- A reduction from baseline of ≥ 4 points in Systemic Lupus Erythematosus Disease Activity Index 2000 (SLEDAI-2K), and
- No new organ system affected, as defined by no new British Isles Lupus Activity Group (BILAG)-2004 grade A and no more than one new BILAG-2004 grade B, and
- No worsening from baseline in subject's lupus disease activity defined by <1 point increase in the Physician's Global Assessment (PGA) [visual analog scale (VAS)] (in the scale of 0-10) and
- No changes to protocol specified medications rules as described below (all criteria must be met):
 - No initiation or increase of SLE standard of care therapy or other disallowed concomitant therapy (see table 8 from latest protocol for protocol-prohibited list).
 - Concomitant corticosteroid dosage at Week 24 to be ≤ 10 mg/day.
 - Concomitant corticosteroid dosage at Week 24 to be \leq Day 1.
 - No increase in corticosteroid dose between weeks 17 and 24.

CONFIDENTIAL

The information contained herein may not be used, disclosed, or published without the written consent of Biogen MA Inc.

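### One Part A dosing bullet holds steroids in Weeks 17-24 at the Week 12 dose; the rest of the section requires the Week 16 dose, so following the bullet after a Week 13-16 taper is a forbidden step-up

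*Protocol*

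**What the plan says.** Protocol 11.4.1.1.2 (Part A specific instructions) makes the oral steroid taper mandatory and states the dosing rules in four places. For Weeks 17-24 they read:

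- **Summary bullet:** "Stable corticosteroid dose (at Week 12 dose) between Week 17 and Week 24".
- **Narrative:** "The dose of prednisone (or equivalent) will remain stable (at the Week 16 dose) between Week 17 and Week 24".
- **Week-by-week rule:** "Stable dosage at Week 16 dosage, no increases or decreases are allowed".
- **Table 7, last row:** "Stable at Week 16 dose".

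For the preceding period, the bullet directly above the first of these allows "Stable Week 12 corticosteroid dose, or decrease by 2.5 mg between Week 13 and Week 16". The narrative leaves that further taper to the investigator.

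Two later rules depend on what happens to the dose. The composite SRI-4 response (Protocol Section 6, Table 4) requires "No increase in corticosteroid dose between Weeks 17 and 24", and SAP 6.3.5 repeats it: "No increase in corticosteroid dose between weeks 17 and 24". SAP 5.8 makes a Part A subject a treatment failure for, among other things, "Subjects with corticosteroid dose increase above baseline during the treatment period except for what is allowed under rescue 1 during week 1 to 4", and has a separate rule for any increase after Week 20.

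**The concern.** Two consecutive bullets, read literally, tell a site to taper in Weeks 13-16 and then go back to the Week 12 dose on Day 114. The same section prohibits that rise, so a site that obeys one line breaks another. The three rescue windows (Weeks 1-4, 5-7 and 9-11) have closed by then, so no rescue provision covers it.

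The result is a protocol deviation produced by the protocol itself. It may also cost an SRI-4 response in a subject who tapered successfully. The subjects exposed are those doing well enough to reduce steroids further, so any lost responses would come from likely responders.

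**Working it through.** No power or error-rate figure bears on this point. The check compares the texts and works out the dose step.

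**1. When the texts differ.** In Weeks 13-16 the dose may only stay level or fall. If it stays level, the Week 12 and Week 16 doses are equal and all four statements agree. If it falls, the bullet and the other three statements give different doses.

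**2. Size of the step.** The Week 12 dose comes from Table 7. The taper of 2.5 mg comes from the Week 13-16 bullet.

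Week 16 dose = Week 12 dose − 2.5

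Step on Day 114 under the bullet = Week 12 dose − Week 16 dose

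| Start (mg/day) | Week 12 | Week 16 after taper | Weeks 17-24 under bullet | Step | Week 12 ÷ start |
|---|---|---|---|---|---|
| 20 | 10 | 7.5 | 10 | +2.5 | 0.50 |
| 17.5 | 7.5 | 5 | 7.5 | +2.5 | 0.43 |
| 15 | 7.5 | 5 | 7.5 | +2.5 | 0.50 |
| 12.5 | 5 | 2.5 | 5 | +2.5 | 0.40 |
| 10 | 2.5 to <5 | 0 to <2.5 | 2.5 to <5 | +2.5 | 0.25 to <0.50 |
| 7.5 | 2.5 | 0 | 2.5 | +2.5 | 0.33 |
| 5 | 2.5 | 0 | 2.5 | +2.5 | 0.50 |
| 2.5 to <5 | 0 to 2.5 | 0 (if Week 12 was 2.5) | 2.5 | +2.5 | at most 1.0 |

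In the 7.5 and 5 mg columns the bullet restarts a steroid the subject had stopped. Under the Week 16 wording the step is 0 mg for everyone.

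**3. SRI-4 steroid-dose conditions.**

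- Week 24 dose at most 10 mg/day: met, because the largest resumed dose is 10.
- Week 24 dose no higher than Day 1: met, because every ratio is at most 1.0.
- No increase in Weeks 17-24: failed, if the change from Day 113 to Day 114 counts as inside the window. Table 7 starts that window on Day 114.

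The third condition is therefore the only steroid-dose condition the step can fail.

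**4. Steroid-dose treatment-failure rules in SAP 5.8 that could apply.**

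- Increase above baseline: not met, from the ratios above.
- Increase after Week 20: not met. The Week 20 visit is Day 141, and 141 − 114 = 27 days later.

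The main treatment-failure trigger in Protocol 16.1.2.1 is likewise an increase from baseline after Week 4, so it is not met either.

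**5. SAP Appendix E.** It lists 10 mg for both Weeks 13-16 and Weeks 17-24, so it does not settle which dose applies.

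**The case against.** The strongest reply is that the protocol largely resolves this itself. The bullets are introduced as a brief recap. The mandatory schedule is Table 7, which agrees with the narrative and with a rule that expressly bars any change in Weeks 17-24. A site would have to prefer one recap line to all of that and raise steroids without a clinical reason. Loss of an SRI-4 response then needs several conditions together: the optional taper, a site following the bullet, every other criterion met, and the Day 113-to-114 change counted as inside the window, which the SAP does not spell out. On this view it is a minor erratum. Deviations are already logged under SAP 5.7.

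Much of this stands. The likelihood is low, no count can be given, and this is a drafting inconsistency and not a contested design decision. The 2.5 mg figure is also one reading: Table 7 allows a decrease without stating its size. A larger taper would make the step larger but would leave the resumed dose, and so steps 3 and 4, unchanged.

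Two points qualify the limits on harm. SAP 5.8 also counts an increase in SLE standard-of-care therapy as failure, and the protocol's background-therapy section lists corticosteroids among permitted standard-of-care treatments. Protocol 11.4.1.1.2 further says that other increases may be treated as failures. Details are deferred to an addendum that is not available here. An effect on the primary analysis is therefore not shown, but it is not excluded.

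None of this removes the contradiction. The bullets are operative dosing text in a mandatory section, and one of them is wrong.

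**Conclusion.** The concern holds. The bullet contradicts three other statements in its own section, and those three identify the intended rule as the Week 16 dose. For a subject who tapered by 2.5 mg in Weeks 13-16, following the bullet means a 2.5 mg/day rise on Day 114. That is a protocol deviation and can lose an SRI-4 response.

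The SRI-4 part assumes that a step taking effect on Day 114 counts as an increase within Weeks 17-24 and that the subject met all other criteria. The number of subjects affected cannot be derived from the documents. The SRI-4 definition is consistent with the majority text and is not at fault. The correction should be made, but no change to the primary result has been demonstrated.

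**What to change.** In the Week 17-24 bullet of the Part A instructions, change Week 12 to Week 16, and send sites a short clarification letter. Leave the SRI-4 definition as it is.

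Before unblinding, list every Part A subject whose dose rose at the start of Week 17 and record each as a protocol deviation. The practical deadline is Interim Analysis 2, when part of the sponsor's study team becomes unblinded; SAP 5.7 only requires deviations to be classified before the later, final database lock.

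The cost is one changed number, one letter and one listing. No design decision is reopened.

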11.4.1.1.3. Pain Medication

11.4.1.1.3.1. Nonsteroidal Anti-inflammatory Treatments

Subjects taking stable doses of NSAIDs (e.g., ibuprofen, naproxen, aspirin) for SLE symptoms at Screening should continue to do so throughout the trial; however, subjects should refrain from using NSAIDs within 24 hours before each study visit. Subjects taking stable doses of NSAIDs for reasons other than SLE are encouraged to titrate down as tolerated.

Low-dose aspirin (<350 mg/day) at stable doses for cardiovascular prophylaxis is permitted during the study.

11.4.1.1.3.2. Acetaminophen

Acetaminophen (paracetamol) may be initiated for pain control of SLE symptoms during the study. The medication should be titrated down as tolerated. The maximum dose of acetaminophen or pain medications that contain acetaminophen is 3 g/day.

11.4.1.1.3.3. Other Pain Medications

Other pain medications, including opiates, other narcotics, and medical marijuana, may be used to treat symptoms of arthritis and other extra-articular conditions in SLE as needed; however, these medications may not be used within 24 hours of a study visit if they are used as needed. If opiates are chronically taken prior to Screening, a stable dose should be maintained from Screening until the end of the Treatment Period.

CONFIDENTIAL

The information contained herein may not be used, disclosed, or published without the written consent of Biogen MA Inc.

11.4.1.1.4. Vitamin D and Calcium Supplements

Use of vitamin D₃ (≥ 400 IU/day) and calcium supplements (≥ 800 mg/day) is recommended for prevention of glucocorticoid- or postmenopausal-induced bone loss. Subjects should continue these medications per SoC with no change in dose during the study.

11.4.1.1.5. Vaccines

Live and live-attenuated vaccines are not permitted within 4 weeks before Screening and throughout the study, and for 16 weeks after the last dose of study treatment.

11.4.1.2. Disallowed Concomitant Therapy

Table 8 provides a list of medications prohibited during study participation (and during the prescribed washout period prior to randomization).

Table 8: Disallowed Concomitant Therapy and Required Washout Periods Prior to Randomization

Generic Name	Washout Period Prior to Randomization
Biologics (monoclonal antibodies and fusion proteins)	
Rituximab, ocrelizumab, other B-cell directed therapies ¹	24 weeks
Abatacept, belimumab, tocilizumab, TNF inhibitors	12 weeks or 5 half-lives (whichever is longer)
Immunosuppressants	
Tacrolimus, pimecrolimus, sirolimus	4 weeks
High-potency topical corticosteroid and/or topical agents (immunosuppressive) for skin lesions	7 days
High-potency intralesional corticosteroids	4 weeks
IV or IM corticosteroids (Parts A and B)	12 weeks
Intra-articular corticosteroids (Part A)	12 weeks
Cyclophosphamide, cyclosporine, mixoribine	12 weeks or 5 half-lives (whichever is longer)
Other	
IV and SC immunoglobulin	12 weeks
Plasmapheresis	12 weeks
Thalidomide or lenalidomide	12 weeks
Investigational or approved agent that blocks IFN- α	24 weeks
Any investigational therapy, including BIIB059, and any not mentioned above	24 weeks

IFN = interferon; IM = intramuscular; IV = intravenous; SC = subcutaneous; TNF = tumor necrosis factor

¹ Subjects with history of B-cell directed therapies more than 24 weeks but less than 52 weeks prior to Screening will be excluded if the total CD19 B-cell level is < 25 cells/ μ L as measured at Screening.

CONFIDENTIAL

The information contained herein may not be used, disclosed, or published without the written consent of Biogen MA Inc.

